7.2.6.2 Handling of dropouts or missing data

For evaluation by visit, on ITT population, a last visit named "Endpoint/LOCF" containing the last observation carried forward (LOCF) will be created.

For Area Under the Curves (of the TSS or for each individual clinical score), no imputation for missing assessment will be done and calculations will be done on observed data, nevertheless for the subjects who terminated earlier, the Final Visit will be imputed to the closest theoretical visit of the protocol.

For patients who have individual score assessments on unscheduled day, closest theoretical visit of the protocol will be used, for each evaluation overtime and AUC.

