5.6 Procedures/Reasons for subject discontinuation

An Investigator may decide to discontinue a subject from the clinical trial for safety reasons.

Protocol No.: RD.03.SPR.112075 V01 16 Aug 2016

Page 38 of 85

Although the importance of completing the entire clinical trial should be explained to the subject by the clinical trial personnel, any subject is free to discontinue participation in this clinical trial at any time and for whatever reason, specified or unspecified, and without any prejudice. No constraints are to be imposed on the subject, and when appropriate, a subject may be treated with other conventional therapy when clinically indicated.

When a subject does not complete the clinical trial, he/she will be fully assessed, if such assessment is possible. The procedures designated for the Early Termination visit should be completed for all subjects discontinuing the clinical trial and the appropriate Case Report Form (CRF) should be completed. The Follow up visit should then occur approximately one week after the Early Termination visit.

All discontinuations and the reason for discontinuation are to be documented by the Investigator on the Exit Form

For discontinuation due to an AE, the Adverse Event Form is to be completed. The Investigator should also ensure that the subject receives suitable therapy for the AE.

A subject who has been randomized and assigned a randomization number cannot be replaced by another subject if he/she discontinues the clinical trial for any reason. Additional subjects could be enrolled (randomized/assigned to treatment) in order to attain the number of evaluable subjects.

GALDERMA may also decide to prematurely terminate or suspend a subject's participation in the clinical trial.

Potential reasons for discontinuation, as listed on the Exit Form, are defined below:

Adverse Event: Complete an Adverse Event Form.

 Withdrawal by Subject:
 Includes consent withdrawal, subject relocation, schedule conflicts, etc. Does not include AE. Explain the reason for withdrawal in the

comment section of the CRF Exit Form.

Protocol Deviation: Explain the deviation in the comment section of the CRF Exit Form.

• Lost to Follow-up: Confirmed with two documented phone calls and a certified letter

(delivery receipt requested) without answer. Explain in the comment

section of the CRF Exit Form.

Other: This category is to be used for a subject who discontinues due to a

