7.2.4. Compliance

extreme cream will be applied at home by the subject twice daily, up to 2 weeks before the treatment period upon the judgment of the dermatologist. The scaling score should be 0 or 1 when the subject is enrolled.

All applications during the treatment period will be performed by a person from the investigational team at the study centre, once daily during 3 weeks, 5 days a week except for the third week, for a total of 14 applications.

Subjects with a low compliance will be excluded from PP population during the data review.

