7.2.5. Efficacy analysis

7.2.5.1 Primary and secondary efficacy analysis

Descriptive statistics will be done on observed cases for PP and ITT populations.

The Area Under the Curve (AUC) will be calculated from Day 1 (before application) to Day 19 by subject and by treatment/pre-treatment on the Z1-Z6 mini-zone, using the trapezoidal rule on ITT and PP population.

Dates of theorical visit will be used to perform AUC.

AUC of TSS will be submitted to an analysis of variance including subject and treatment/pretreatment as factors in the model, ^{CCI}

AUC of individual clinical scores (erythema, scaling and induration) will be submitted to the same variance analysis.

TSS and TSS percent change from day 1 will be descriptively summarized by visit, as the individual score of erythema, scaling and induration and their respective change from day 1. The analysis will be performed on PP population and ITT population (baseline and Endpoint/LOCF) Success will be presented in frequency tables (N,%) by treatment/pre-treatment and by visit. The time to first success will be summarized by treatment/pre-treatment.

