9.2.3. Primary and secondary efficacy criteria

Table. AUC of TSS – Treatment period - PP and ITT population

		CD10367 placebo pre-treated	CD10367 3% pre-treated	CD10367 placebo	CD10367 1%	CD10367 3%	Betneval 0.1%
AUC of TSS (PP)	Ν		_				
	Mean						
	SD						
	Median						
	(Min,Max)						
AUC of TSS (ITT)	N						
	Mean						
	SD						
	Median						
	(Min,Max)						

Table. Analysis of variance for AUC of TSS – Treatment period - PP population

		LSmean(SE)	p-value*
Model Effects	Patient	-	
Treatment	CD10367 placebo pre-treated		
Treatment	CD10367 3% pre-treated		
Contrast	 CD10367 placebo – Betneval		
CCI			

Internally Approved 01-Feb-2019 Protocol No: RD.03.SPR.112075

Statistical Analysis Plan Page 23 of 38

Table. AUC of erythema – Treatment period - PP and ITT population

Table. Analysis of variance for AUC of erythema – Treatment period - PP population

Table. AUC of scaling – Treatment period - PP and ITT population

Table. Analysis of variance for AUC of scaling – Treatment period - PP population

Table. AUC of induration – Treatment period - PP and ITT population

Table. Analysis of variance for AUC of induration – Treatment period - PP population

Table. TSS and TSS percent change from day 1 – PP population

TSS		CD10367 placebo pre-treated	CD10367 3% pre-treated	CD10367 placebo	CD10367 1%	CD10367 3%	Betneval 0.1%
Screening	N						
	Mean SD						
	Median						
	(Min,Max)						
End of pre-treatment period*							
Day 1, Day 4	Ν						
	Mean						
	SD						
	Median						
Percent change from Day 1 at Day 4	(Min,Max) N						
reicent change nom Day 1 at Day 4	Mean						
	SD						
	Median						
	(Min,Max)						
Day 8, Day 11, Day 15, Day 19	N						
Percent change from Day 1 at Day	Ν						
8, Day 11, Day 15, Day 19							
	•••						

*performed only in Z1 and Z2

Internally Approved 01-Feb-2019 Protocol No: RD.03.SPR.112075

CONFIDENTIAL GALDERMA

Statistical Analysis Plan

Page 24 of 38 Table. TSS and TSS percent change from day 1 – ITT population

ITT population and with only 2 visits: Day 1 and Endpoint/LOCF

Table. Erythema and change from day 1 – PP population

 Table. Erythema and change from day 1 – ITT population

 Table. Scaling and change from day 1 – PP population

Table. Scaling and change from day 1 –ITT population

 Table. Induration and change from day 1 – PP population

Table. Induration and change from day 1 - ITT population

Table. Clearing score by visit – Treatment period - PP population

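### SAP 7.2.6.2 lets an early leaver's Day 1 to Day 19 AUC cover only 3, 7, 10 or 14 of 18 days, which distorts the ITT AUC summaries and shrinks real treatment differences

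*SAP*

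**What the plan says.** - **Endpoint.** Protocol 7.1.2.1 and SAP 4.1 define the primary criterion as the AUC of TSS over Day 1 to Day 19. Scores are taken on Days 1, 4, 8, 11, 15 and 19, and at an early termination visit.
- **Calculation.** SAP 7.2.5.1 applies the trapezoidal rule by subject and zone, in ITT and PP, on planned days: "Dates of theorical visit will be used to perform AUC".
- **Missing data.** For the AUCs, SAP 7.2.6.2 states "no imputation for missing assessment will be done and calculations will be done on observed data". For early leavers, "the Final Visit will be imputed to the closest theoretical visit of the protocol". The section shows no blacked-out text.
- **By-visit summaries.** The same section sets a separate ITT rule, an Endpoint visit "containing the last observation carried forward (LOCF) will be created".
- **Tables (SAP 9.2.3).** The descriptive table is "AUC of TSS – Treatment period - PP and ITT population". The test table is "Analysis of variance for AUC of TSS – Treatment period - PP population".
- **PP membership.** SAP 5.2 removes subjects with major deviations, decided at a blind review. Early termination is not among its examples. If nobody has a major deviation, PP equals ITT. SAP 7.2.4 adds: "Subjects with a low compliance will be excluded from PP population during the data review", without a threshold.

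**The concern.** An AUC is a level multiplied by a duration. If the duration differs between subjects and is not corrected, the AUC partly measures time in study. Here the error runs in a misleading direction: lower is better, and leaving early lowers the value. An unimproved zone in a leaver can therefore show a smaller AUC than an improved zone in a completer. Someone reading N, mean, SD, median and range could not see this.

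Two things are at stake. The first is the ITT summary of the primary endpoint. The second is the contrasts with vehicle: if leavers stay in the analysed set, the part of the curve where a growing effect would show is missing for them.

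**Working it through.** The documents give no figure for a truncated AUC to reproduce, and the basis for the 24 subjects is blacked out. From the documents I use the six scoring days, the trapezoidal rule and N = 24. My assumptions are a vehicle TSS constant at 7, 1 to 3 leavers, and two shapes for the active-vehicle difference: linear from 0 at Day 1 to 4 points at Day 19, or a plateau of 4 points from Day 4 on.

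**1. One subject, constant TSS.** AUC = TSS × (last day − 1). The full value is 7 × 18 = 126.

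| Exit day | Days covered | Share of full | AUC at TSS 7 |
|---|---|---|---|
| 4 | 3 | 16.7% | 21 |
| 8 | 7 | 38.9% | 49 |
| 11 | 10 | 55.6% | 70 |
| 15 | 14 | 77.8% | 98 |

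A completer whose TSS falls linearly from 7 to 3 has AUC 18 × (7 + 3)/2 = 90. The unimproved Day 8 leaver, at 49, looks better.

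**2. ITT mean and SD for m leavers.** Mean = 126 − (m/24) × (126 − truncated AUC). SD from truncation alone = (126 − truncated AUC) × √[m(24 − m)/(24 × 23)].

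| Exit day | Mean, m = 1 to 3 | SD from truncation alone |
|---|---|---|
| 4 | 121.6 to 112.9 | 21.4 to 35.5 |
| 8 | 122.8 to 116.4 | 15.7 to 26.0 |
| 11 | 123.7 to 119.0 | 11.4 to 18.9 |
| 15 | 124.8 to 122.5 | 5.7 to 9.5 |

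This SD does not simply add to a real one. With a true SD of 18 (assumed) and one Day 8 leaver, the total is about √(18² + 15.7²) = 23.9.

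**3. Differences between zones.** With no effect, both zones lose the same area and the difference stays 0. With an effect, the higher zone loses more. At Day 8 exit under the linear shape, the vehicle loses 126 − 49 = 77.0 and the active zone 90 − 43.6 = 46.4, so that subject's difference falls by 30.6, from 36 to 5.4.

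Shrinkage of the mean difference = (m/24) × (1 − share kept).

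| Exit day | Linear: kept of 36 | Shrinkage, m = 1 to 3 | Plateau: kept of 66 | Shrinkage, m = 1 to 3 |
|---|---|---|---|---|
| 4 | 1.0 | 4.1% to 12.2% | 6 | 3.8% to 11.4% |
| 8 | 5.4 | 3.5% to 10.6% | 22 | 2.8% to 8.3% |
| 11 | 11.1 | 2.9% to 8.6% | 34 | 2.0% to 6.1% |
| 15 | 21.8 | 1.6% to 4.9% | 50 | 1.0% to 3.0% |

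Protocol 5.6 allows extra subjects "in order to attain the number of evaluable subjects". Three Day 4 leavers among 27 give 3/27 × (1 − 1/36) = 10.8%.

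**4. ANOVA residual.** The subject factor removes the common drop in level but not the unequal contrasts. With 2 of 24 leaving at Day 8 (linear), the contrast varies between subjects with SD 30.6 × √(2/24 × 22/24) = 8.4 AUC points from truncation alone. This spread goes into the residual.

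**5. The closest-visit rule.** Day 17 is two days from both Day 15 and Day 19. Exits on Days 2, 5, 9, 12 and 16 point to Days 1, 4, 8, 11 and 15, which are already filled if attended. If the nearest visit was missed, Protocol 6.3.4 moves its evaluation to the next visit and the rule works.

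**The case against.** **The SAP chose this rule deliberately.** It limits LOCF to by-visit evaluation and sets an observed-data rule for AUC, and SAP 7.2.5.1 speaks of observed cases. This stands: a reader might infer that the SAP breaks its own LOCF rule, but these are two separate rules. The defect is that the AUC rule does not deliver the defined endpoint.

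**The comparison is within subject.** A reader might infer that truncation creates a false difference. It does not, because all six zones are cut at the same visit. Nor does stopping treatment on one zone for poor tolerance trigger it, since Protocol 7.1.1.1 keeps scoring that zone. It is not neutral either: when zones differ, the loss falls more on the higher-scoring vehicle, so a real effect looks smaller.

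**The tests are on PP.** This limits the reach but does not close the route. A Day 8 leaver has had 5 of 14 applications and may be excluded for low compliance, but no threshold is set. Early termination is not a listed deviation, and PP equals ITT if there are no major deviations.

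**The effect is conditional.** No dropout rate is visible, and the study is short and exploratory, with applications made at the site. This stands. The TSS of 7 is also only illustrative, and less apt for the two pre-treated zones, which enter with scaling 0 or 1.

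**Conclusion.** The point holds and is minor. As written, the rule reports an area over 3, 7, 10 or 14 days as an 18-day AUC. If anyone leaves early, the certain effect is on the ITT AUC mean, SD and minimum. ITT differences between treatments also shrink when a true effect exists. The ANOVA contrasts shrink only if leavers remain in the analysed set.

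The shrinkage is about 1% to 12% for 1 to 3 of 24 leaving between Day 4 and Day 15. It rests on the assumed linear and plateau effects and on assumed leaver counts. The fractions of the full AUC depend only on the visit days and constant TSS. The documents do not support a claim that the primary test is invalid or that a spurious benefit would appear: the bias in the contrasts is toward zero.

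**What to change.** Put every AUC on the same 18-day basis. In SAP 7.2.6.2, for the TSS, erythema, scaling and induration AUCs:

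> For subjects who terminate early with at least one score assigned to Day 4 or later, the last observed score is carried forward to Day 19 before the trapezoidal rule is applied. As a sensitivity analysis, AUC = 18 × (observed trapezoidal area) / (theoretical day of last visit − 1). A subject with no score assigned to Day 4 or later has a missing AUC. If the closest visit is already filled, the scheduled score is kept and the early-termination score is the value carried forward; it never replaces the Day 1 score. A Day 17 score is assigned to Day 19 if Day 15 is filled, otherwise to Day 15.

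This takes SAP wording and a few lines of code. It needs no new data, and completers' values do not change.

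The cost is that either rule assumes something about the unobserved part of the curve and gives leavers a noisier AUC. With equal visit-error variances and independent visits, a completer's trapezoid weights (1.5, 3.5, 3.5, 3.5, 4, 2) have sum of squares 59. Under LOCF, a Day 8 leaver's weights (1.5, 3.5, 13) give 183.5, or 3.1 times as much, and a Day 4 leaver's (1.5, 16.5) give 274.5, or 4.7 times. At a between-visit correlation of 0.5, the variance is half the sum of squares plus half of 18², and the ratios fall to 253.75/191.5 = 1.3 and 299.25/191.5 = 1.6. The gain is a correctly labelled, less biased AUC. I make no claim about power, because the net effect on precision depends on a visit-error SD that the documents do not show.

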7.2.6.3 Interim analyses and data monitoring

Not Applicable (NA)

7.2.0.4 Municemer studies	7.2.6.4	Multicenter studies
---------------------------	---------	---------------------

NA

7.2.6.5	Multiple comparison/multiplicity
CCI	
7.2.6.6 NA	Use of an efficacy subset of patients
7.2.6.7 NA	Active-Control studies intended to show equivalence

7.2.6.8 Examination of Subgroups

NA

7.3. Safety analysis

All safety data will be summarized based on the safety population.

7.3.1. Extent of exposure

Number of days of keratolytic during the pre-treatment period in zone 1 and 2 will be summarized.

Study product application will be presented by treatment/pre-treatment and by visit.

Number of study products applications will be summarized by treatment/pre-treatment.

7.3.2. Local tolerance

Local individual signs/symptoms (irritation, skinging/burning, pruritus) in term of frequency distribution and in quantitative description and the worst score (from Day 2 to Day 19/ET) over time of each individual sign/symptom will be calculated by study product.

7.3.3. Adverse events

Adverse Events will be tabulated by study treatment/pre-treatment and in overall.

Occurrence of adverse events will be separated in two periods: the pre-treatment period from the beginning of the pre-treatment period to day 1 excluded, and the treatment period from the date of first application of study drugs to the end of the study.

For the pre-treatment period, only a table with the overview of the adverse events and a listing of the adverse events during this period will be performed.

For the treatment period, Adverse Events (AE) will be tabulated in frequency tables by System Organ Class (SOC) and Preferred Term (PT) based on MedDRA version 18.0. Additional summary tables will be provided for Adverse Events that are considered serious (SAEs), related to study product, related to protocol procedure, related to the study (study product and/or protocol procedure), Adverse Events of special interest, and Adverse Events leading to discontinuation.

Due to the intra-individual study design and whenever possible (known from CRF) AE will be imputed to the treated area, when not possible then the AE will be imputed to all treated zones.

AEs with an onset prior to the pre-treatment period will be listed separately.

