3 OVERALL CLINICAL TRIAL DESCRIPTION

3.1 Overall description

This is an exploratory, single-centre, investigator blinded, randomized, controlled, intraindividual study, involving approximately 24 subjects with psoriasis vulgaris meeting specific inclusion/exclusion criteria.

The study will be conducted in France and consists of:

a screening period (within 3 weeks before pretreatment period);

Protocol No.: RD.03.SPR.112075 V01 16 Aug 2016

Page 28 of 85

- A pretreatment period 1 week before Baseline visit in order to decrease the scaling on selected target psoriasis plaque(s), before treatment with IMPs. This period can be extended to 2 weeks if sufficient desquamation does not occur and the scaling score does not reach 0 or 1 (none or mild scaling). During this period, the subjects will apply a keratolytic product at home twice a day on the selected plaque(s).
- a 3-week treatment period during which the treatments will be applied on mini-zones according to the randomization list,
- a final visit at Day 19 (or early termination visit if any), to evaluate safety and efficacy of the treatments, **CCI**
- CCI

In total, for each subject six-treatment mini-zone will be tested:

- on one or more psoriatic plaque, four mini-zones will be tested:
 - o CD10367 3% solution
 - o CD10367 1% solution
 - o CD10367 solution placebo
 - o Betneval 0.1% ointment
- on one or two desquamated psoriatic plaque (pre-treated), two mini-zones will be tested:
 - o CD10367 3% solution
 - o CD10367 solution placebo

[figure not shown]

[figure not shown]
Figure 1: Schematics of the treated mini-zones

Protocol No.: RD.03.SPR.112075 V01 16 Aug 2016

Page 29 of 85

Local tolerance assessments will be performed twice a week from Day 2 to Day 19/ET visit and at any visit if a cutaneous AE occur on a treated zone.

Psoriasis severity scores will be performed at screening visit before desquamation, then two times a week from Day 1 to Day 19/ET.

All samples will be shipped to GALDERMA R&D or its contractors at the end of the study.

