7.2.5 Local tolerability assessment

Local tolerability assessment will be performed using the following twice a week from Day2 to Day 19/ET visits scales two times per week during the treatment period. If at any visit, a treatment leads to discontinue applications either temporarily or permanently, an AE must be declared, and local tolerability assessments and photos of the concerned zone must be performed even if it was not planned in study flowchart for this visit. Grading for local tolerability assessments will take into consideration the time period from the last local tolerability assessment up to the current visit. The worst severity since the previous visit will be recorded. Local tolerability (Irritation, stinging/burning, pruritus) will be assessed separately on each minizone using the following scales:

Protocol No.: RD.03.SPR.112075 V01 16 Aug 2016

Page 52 of 85

Table 7 Local tolerance 4-point scales

Irritation	Skin irritati	n Assessment						
0	None:	o signs of irritation						
1	Mild:	Slight signs of irritation						
2	Moderate:	Moderate signs of irritation: Obvious increase in redness as compared to the non-treated surrounding area						
3	Severe:	Severe signs of irritation						
Stinging/ Burning	Prickling p	ain sensation						
0	None:	No stinging/burning						
1	Mild:	Slight warm, tingling/stinging sensation; not really bothersome						
2	Moderate:	Definite warm, tingling/stinging sensation that is somewhat bothersome						
3	Severe:	Hot, tingling/stinging sensation that causes severe discomfort						
Pruritus	Itch sensat	tion						
0	None:	No itching						
1	Mild:	Itching is noticeable but not really bothersome						
2	Moderate:	Definite itching that is somewhat bothersome						
3	Severe:	Marked itching, urge to scratch and causes definite discomfort						

Irritation, will be clinically evaluated by the Investigator. The Investigator will record stinging/burning and pruritus after discussion with the subject. The severity of stinging/burning sensation occurring after the last drug application before the visit will be asked. The Investigator will ask an open-ended question, taking care not to influence the subject's answer, such as "Have you experienced any sensations such as stinging/burning?"

An Adverse Event page must be completed if the severity of the signs and symptoms is such that:

- The subject temporary or permanently discontinues the treatment at his/her request or at the Investigator's request.

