7.2.6.1.3 Adverse Events of Special Interest (AESIs)

An AESI is a noteworthy event for the particular study drug that can be appropriate to monitor closely. It could be serious or non-serious and AESIs could include events that might be potential precursors or prodromal symptoms for more serious medical conditions in susceptible individuals.

The AESIs for this protocol have been pre-defined as follows:

- Suspected sensitization or photosensitization
- Any non-dermatological treatment-emergent related adverse events (AE), including:
 - Increase in QTc interval from Baseline >60msec or a value>500msec at D19/ET ECG assessed as related to the study drug
 - Out-of-range laboratory results that are identified as both clinically significant and related to the study drug(s)
 - Any treatment-emergent signs/symptoms suggestive of keratitis or corneal ulceration (e.g. pain of the eye, injected/red eye, blurred vision, etc.), or treatment-emergent keratitis or corneal ulceration diagnosed at the ophthalmological examination, or any other treatment-emergent acute ophthalmological findings assessed as related to the study drug
- Any dermatological treatment-emergent related adverse events (AE) leading to permanent treatment discontinuation on any zone
- Treatment-emergent skin rash assessed as related to the study drug, defined as a papulopustular eruption commonly described as acneiform eruption

For AESIs, the Investigator is required to complete the Adverse Event Form on the CRF and follow the AESI reporting procedures in Section 7.2.6.2.3 even if the event is considered non-serious according to the usual regulatory criteria.

Protocol No.: RD.03.SPR.112075 V01 16 Aug 2016

Page 55 of 85

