9.1.3 Data presentation and graphics

The subject disposition, demographics, baseline characteristics, previous therapies, concomitant therapies will be summarized by descriptive statistics.

All efficacy variables will also be summarized by treatment (treatment / pre-treatment) at each visit. The categorical variables will be summarized by frequency and percentage for each response category (N, %). The continuous variables will be summarized using means, medians, minimum, maximum, and standard deviations for the data collected at each visit.

The area under the curve of the TSS (sum of individual clinical scores erythema, induration/plaque elevation and scaling), as well as those of each individual clinical score will be calculated from Day 1 (before application) up to Day 19 by subject and by treatment, using the trapezoidal rule.

The time to success (defined as a clearing score of 0 or 1) will be summarized by treatment. Only the earliest day of success will be considered in defining the time to partial clearing, independently of the subsequent days.

The local tolerance scores will be summarized using frequency and percentage by visit and study product. The worst scores will also be summarized.

Adverse Events will be tabulated by study treatment. Adverse Events will be tabulated in frequency tables by System Organ Class (SOC) and Preferred Term (PT) based on the MedDRA dictionary. Additional summary tables will be provided for Adverse Events that will be considered as severe, serious (SAEs) and Adverse Events leading to discontinuation. Any AE and related AE will be summarized for each category. Analyses of adverse events will be based on Treatment Emergent Signs and Symptoms (TESS) *i.e.* adverse events occurring on the day of, or after, treatment application (Baseline).

Events having occurred before the day of treatment application (i.e. before Baseline) will be listed only.

Due to the intra-individual study design and whenever possible (known from e-CRF), AE will be imputed to the treated area, when not possible then the AE will be imputed to all treated area.

Physical examination, vital signs, ECG and ophthalmic examination will be summarized by descriptive statistics.

Shift tables for the laboratory data (and urinalysis) will be tabulated for each laboratory parameter.

Protocol No.: RD.03.SPR.112075 V01 16 Aug 2016

Page 75 of 85

Pharmacokinetics parameters will be descriptively summarized.

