9.3.3. Adverse events

Table. Overview of adverse events during the pre-treatment period – Safety population Table. Listing of adverse events during the pre-treatment period – Safety population Table. Listing of adverse events prior the pre-treatment period – Safety population †Or listing if few AE. Table. Overview of adverse events during the treatment period – Safety population Table *†*. Summary of adverse events by Preferred Term – Safety population Table †. Summary of adverse events Related to the study drug by Preferred Term – Safety population Table †. Summary of adverse events Related to the protocol procedure by Preferred Term – Safety population Table †. Summary of adverse events Related to the study by Preferred Term – Safety population Table . Summary of adverse events by System Organ Class and Preferred term – Safety population Table †. Summary of adverse events Related to the study drug by System Organ Class and Preferred term – Safety population Table †. Summary of adverse events Related to the protocol procedure by System Organ Class and Preferred term – Safety population Table †. Summary of adverse events Related to the study by System Organ Class and Preferred term – Safety population Table †. Summary of adverse events by severity by System Organ Class and by Preferred term – Safety population Table †. Summary of adverse events Related to the study drug by severity by System Organ Class and by Preferred term – Safety population Table †. Summary of adverse events Related to the protocol procedure by severity by System Organ Class and by Preferred term – Safety population Table †. Summary of adverse events Related to the study by severity by System Organ Class and by Preferred term – Safety population Table †. Summary of serious adverse events by System Organ Class and by Preferred term – Safety population Table †. Summary of adverse events leading to discontinuation by System Organ Class and by Preferred term – Safety population

Table †. Summary of AESIs by System Organ Class and by Preferred term – Safety population

Statistical Analysis PlanPage 32 of 38**9.3.4.**Vital Signs, Physical Findings

Table. Physical examination – Safety population

		Screening	DAY 19/ET
Physical examination	Ν		
	Normal		
	Abnormal and Not clinically significant		
	Abnormal and Clinically significant		

Table. Shift table of Physical examination – Safety population

	Day 19/ET		

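### Adverse events that cannot be tied to a zone are counted under all six treatments, so non-zone rows are identical across columns and pooled active-to-vehicle ratios are pulled towards 1

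*SAP*

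**What the plan says.** Protocol 3.1 sets the design: "In total, for each subject six-treatment mini-zone will be tested". Four zones lie on ordinary plaques (CD10367 3%, CD10367 1%, placebo, Betneval) and two on desquamated plaques (3%, placebo). All are treated over the same three weeks.

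SAP 7.3.3 fixes the columns of the AE tables: "Adverse Events will be tabulated by study treatment/pre-treatment and in overall". An event goes to its zone when the CRF identifies one; otherwise, "when not possible then the AE will be imputed to all treated zones". Protocol 9.1.3 has the matching sentence: "when not possible then the AE will be imputed to all treated area". Neither document gives events without a zone a column of their own or marks them in the tables.

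The rule carries into the tables of related, serious, discontinuation and special-interest events, which include "Summary of AESIs by System Organ Class and by Preferred term" (SAP 9.3.3). The AESI list in protocol 7.2.6.1.3 has four top-level classes. One has no zone: "Any non-dermatological treatment-emergent related adverse events (AE), including" QTc, laboratory and ocular findings. Another is zone-specific by its wording: "Any dermatological treatment-emergent related adverse events (AE) leading to permanent treatment discontinuation on any zone". The remaining two are suspected sensitization or photosensitization, and related papulopustular rash.

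**The concern.** A systemic event belongs to the subject. When six products are used at once, it cannot be assigned to one of them. The rule turns that missing information into six equal treatment-specific counts. A reader of the AE table sees the same rate under active, vehicle and comparator and may take it as a finding of no difference, when the equality comes from the counting rule.

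Two results are affected. First, a systemic event judged related to study drug is reported as a related event of placebo and of Betneval. Second, the same events enter the pooled rows of each column and dilute the relative contrast for zone-tied events, which are the ones this design can attribute. Safety stands beside efficacy in the primary objective (protocol 2.1, SAP 1), so the AE tables are part of the main result.

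**Working it through.** The documents state no AE rate and show no test on AEs, so there is no planned figure to reproduce. The inputs from the documents are six zones per subject (protocol 3.1), 24 subjects planned to be randomized (protocol 9.2) and the imputation rule. All event rates below are assumptions.

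**1. Rows made only of non-zone events.** If s subjects have such an event, every column shows s/24. The difference is 0 and the ratio is 1 for any true drug effect. For s = 3, each of the six columns shows 3/24 = 12.5%, and 3 subjects produce 3 × 6 = 18 column entries.

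**2. Pooled rows, no overlap.** Assume zone-tied AEs in 4 of 24 subjects on 3% and 0 of 24 on vehicle, and s other subjects with a non-zone AE. The active column shows (4 + s)/24 and the vehicle column s/24.

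| s | Active | Vehicle | Ratio | Difference |
|---|---|---|---|---|
| 0 | 4/24 | 0/24 | undefined | 4/24 |
| 3 | 7/24 | 3/24 | 2.33 | 4/24 |
| 6 | 10/24 | 6/24 | 1.67 | 4/24 |
| 12 | 16/24 | 12/24 | 1.33 | 4/24 |

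**3. Pooled rows, independence.** Let q be the proportion of subjects with a non-zone AE, independent of zone-tied AEs at rates pA and pV. Each column shows q + (1 − q)p, so the difference is (1 − q)(pA − pV) and the ratio is [q + (1 − q)pA] / [q + (1 − q)pV]. With pA = 6/24 and pV = 1/24:

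| q | Active | Vehicle | Ratio | Difference (points) |
|---|---|---|---|---|
| 0 | 25.0% | 4.2% | 6.0 | 20.8 |
| 10% | 32.5% | 13.8% | 2.36 | 18.8 |
| 25% | 43.8% | 28.1% | 1.56 | 15.6 |
| 50% | 62.5% | 52.1% | 1.20 | 10.4 |

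With 40% against 10% instead, the ratio is 4.0 at q = 0, 1.69 at q = 25% and 1.27 at q = 50%.

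**4. How overlap matters.** Keep 6 against 1 and add six subjects with a non-zone AE. With no overlap the table shows 12 against 7: ratio 12/7 = 1.71, difference 5/24, unchanged. If the one vehicle-zone subject is among the six with an active-zone AE, and the non-zone AEs fall in exactly those six, it shows 6 against 6: ratio 1, difference 0. The difference therefore shrinks only where the same subjects have both kinds of event.

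The pull on the ratio is also not a strict law. If the vehicle-zone AE is in a seventh subject and only that subject has a non-zone AE, the counts are 7 against 1, and the ratio rises from 6 to 7. That needs non-zone events to fall selectively on subjects whose only zone-tied AE is on vehicle. Under no overlap or independence the ratio moves towards 1.

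**5. Rows not touched.** A preferred-term row made only of zone-tied events receives no imputed count and keeps its original contrast.

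**The case against.** The case for leaving the rule alone has real substance.

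- **The design is the cause.** No rule can assign a systemic event to one of six simultaneous products. Counting it under each is pre-specified, disclosed, and keeps it visible in the active columns. This stands, and a separate column recovers no lost attribution. But the rule is cautious only for each product's absolute count. For the comparison with vehicle it shows an unknown as an equality.
- **Systemic safety is reported elsewhere.** SAP 7.3.4 to 7.3.8 summarize QTc, ophthalmic, laboratory and vital-sign data by visit, and the visible shells have no treatment columns. The Overall AE summary counts each subject once. A reader might infer that the plan hides a systemic signal; it does not. These outputs leave the treatment columns as they are.
- **Zone-level safety has its own measure.** Protocol 7.2.5 states "Local tolerability (Irritation, stinging/burning, pruritus) will be assessed separately on each minizone", and the rule does not reach those scores.
- **Listings may replace tables.** SAP 9.3.3 allows this for the related, serious, discontinuation and AESI tables when few AEs occur, and protocol 1.4 does not expect systemic toxicity. That could remove much of the problem. However, few is not defined, and the treatment-period overview table does not carry the mark.

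Three stronger readings are tempting. One is that every AE and AESI table is forced towards no difference; rows of zone-tied terms are not. Another is that most pre-defined AESIs are non-dermatological; that is one of four top-level classes, although an open-ended one. The third is that the treatment columns feed a formal comparison; the visible AE outputs are descriptive.

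**Conclusion.** The point holds within limits and is minor to moderate. For non-zone rows the equality across columns is certain, because it follows from the rule alone. For pooled rows the direction is towards a ratio of 1 unless overlap is unusually selective. The size cannot be known from the documents: the illustrative ratios of 2.3 to 1.3 rest on an assumed 4/24 against 0/24, a safety population of all 24 subjects and no overlap.

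A reader might infer that the risk difference is always diluted. It is not: in that example it stays at 16.7 points. What remains is a reporting rule that shows unattributable events as equal treatment-specific rates, and as related events of vehicle and comparator, in a trial with safety in its primary objective.

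**What to change.** In SAP 7.3.3, and in the matching sentence of protocol 9.1.3:

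- Tabulate by treatment only AEs located on a treated zone.
- Show all other AEs once per subject, in a separate column headed 'not attributable to a zone'.
- Keep the Overall column.
- Use the same layout for the related, serious, AESI and discontinuation tables, and flag these events in the same way in any listing that replaces a table.

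On the assumed 6/24 against 1/24, the treatment columns would then show a ratio of 6.0 and a difference of 20.8 points whatever the number of non-zone events, and s such subjects would appear once as s/24.

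The cost is a change of wording and one extra column in the shells. It should need no new data, because the present rule already depends on knowing from the CRF whether an event has a zone; the CRF itself was not available to check. The drawback is that a reader who wants the full AE burden of subjects exposed to an active product must look at the new column or at Overall. Additivity is not lost: the treatment columns already fail to sum to Overall, since a non-zone event counts six times across them and once in Overall.
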